4.6.3 Study and Site Discontinuation

The Sponsor has the right to terminate this study or any cohort at any time. Reasons for terminating the study may include, but are not limited to, the following:

- The incidence or severity of adverse events in this or other studies indicates a potential health hazard to patients
- Patient enrollment is unsatisfactory – Recruitment in each cohort will be monitored regularly. After a cohort has been opened for at least 4 months, it may be closed early if the recruitment is less than 2 patients per month on average from the opening of the cohort.

The Sponsor will notify the investigator if the Sponsor decides to discontinue the study or close a cohort.

The Sponsor has the right to close a site at any time. Reasons for closing a site may include, but are not limited to, the following:

- Excessively slow recruitment
- Poor protocol adherence
- Inaccurate or incomplete data recording
- Non-compliance with the International Conference on Harmonisation (ICH) guideline for Good Clinical Practice
- No study activity (i.e., all patients have completed and all obligations have been fulfilled)

5. ASSESSMENT OF SAFETY

5.1 SAFETY PLAN

Atezolizumab (TECENTRIQ[®]) is approved for the treatment of urothelial carcinoma, NSCLC, small cell lung cancer (SCLC) and triple-negative breast cancer (TNBC).

Human experience is currently ongoing and the entire safety profile is not known at this time. The following information is based on results from nonclinical and clinical studies and published data on similar molecules.

Measures will be taken to ensure the safety of patients participating in this trial, including the use of stringent inclusion and exclusion criteria (see Section 4.1.1 and 4.1.2) and close monitoring (as indicated below and in Section 4.5).

Administration of Atezolizumab will be performed in a setting with emergency medical facilities and staff who are trained to monitor for and respond to medical emergencies. All adverse events and serious adverse events will be recorded during the trial and for up to 90 days after the last dose of study drug or until the initiation of another anti-cancer therapy, whichever occurs first. To mitigate potential unknown risks, at least in part,

dosing beyond Cycle 1 will be limited to patients who have not developed unacceptable toxicity or disease progression or who have evidence of potential pseudoprogression/tumor immune infiltration. The potential safety issues anticipated in this trial, as well as measures intended to avoid or minimize such toxicities, are outlined in the following sections.

5.1.1 Risks Associated With Atezolizumab

The PD-L1/PD-1 pathway is involved in peripheral tolerance; therefore, such therapy may increase the risk of immune-mediated adverse events, specifically the induction or enhancement of autoimmune conditions.

Atezolizumab has been associated with risks such as the following: IRRs and immune-mediated hepatitis, pneumonitis, colitis, pancreatitis, diabetes mellitus, hypothyroidism, hyperthyroidism, adrenal insufficiency, hypophysitis, Guillain-Barré syndrome, myasthenic syndrome or myasthenia gravis, meningoencephalitis, myocarditis, nephritis, and myositis. Immune-mediated reactions may involve any organ system and may lead to hemophagocytic lymphohistiocytosis and macrophage activation syndrome.

Refer to Appendix 8 and Section 6 of the Atezolizumab Investigator's Brochure for a detailed description of anticipated safety risks for atezolizumab.

5.1.2 General Plan to Manage Safety Concerns

5.1.2.1 Eligibility Criteria

Eligibility criteria were selected to guard the safety of patients in this trial. Results from the nonclinical toxicology studies with Atezolizumab, as well as the nonclinical/clinical data from other PD-L1/PD-1 inhibitors, were taken into account. Specifically, patients at risk for study-emergent autoimmune conditions or with a prior diagnosis of autoimmune disease, patients with evidence of acute infections, and patients who have received a live-attenuated viral vaccine within 4 weeks of Cycle 1 Day 1 are excluded from the study (see Section 4.1.2 for additional details).

5.1.2.2 Monitoring

Safety will be evaluated in this study through the monitoring of all serious and non-serious adverse events defined and graded according to NCI CTCAE, v4.0. Patients will be assessed for safety (including laboratory values) according to the Schedule of Assessments ([Appendix 1](#)). Laboratory values must be reviewed prior to each infusion.

General safety assessments will include serial interval histories, physical examinations, and specific laboratory studies, including serum chemistries and blood counts (see [Appendix 1](#) and [Appendix 2](#) for the list and timing of study assessments).

During the study, patients will be closely monitored for the development of any signs or symptoms of autoimmune conditions and infection.

All serious adverse events and protocol-defined events of special interest (see Sections 5.2.2 and 5.2.3) will be reported in an expedited fashion (see Section 5.4.2).

Patients will be followed for safety for 90 days following their last dose of study drug or until they receive another anti-cancer therapy, whichever comes first.

Patients who have an ongoing study drug-related adverse event upon study completion or at discontinuation from the study will be followed until the event has resolved to baseline grade, the event is assessed by the investigator as stable, new anti-cancer treatment is initiated, the patient is lost to follow-up, the patient withdraws consent, or it has been determined that study treatment or participation is not the cause of the adverse event.

5.1.3 Atezolizumab Dose Modification

There will be no dose reduction for Atezolizumab in this study. Patients may temporarily suspend study treatment if they experience adverse events that require a dose to be held. If Atezolizumab is held because of adverse events for > 105 days beyond when the next dose would have been given, then the patient will be discontinued from Atezolizumab treatment and will be followed for safety and efficacy as specified in the Schedule of Assessments ([Appendix 1](#)).

If a patient must be tapered off steroids used to treat adverse events, Atezolizumab may be held for additional time beyond 105 days. The acceptable length of interruption will depend on an agreement between the investigator and the Medical Monitor.

Dose interruptions for reason(s) other than adverse events, such as surgical procedures, may be allowed with Medical Monitor approval. The acceptable length of interruption will depend on agreement between the investigator and the Medical Monitor.

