- Uni-dimensional measurements were included to obtain the total tumor measurement
- A confirmed response required repeat observation on 2 occasions 4 weeks apart

¹ Byrne MJ, Nowak AK. Modified RECIST criteria for assessment of response in malignant pleural mesothelioma. Ann Oncol. 2004 Feb;15(2):257-60.

Appendix 7

Malignant Pleural Mesothelioma Response Evaluation Criteria (cont.)

The RECIST definition is listed in the table below

Complete response (CR)	Disappearance of all target lesions with no evidence of tumors elsewhere
Partial response (PR)	At least a 30% reduction in the total tumor measurement
Progressive disease (PD)	Increase of at least 20% in the total tumor measurement over the nadir measurement or the appearance of one or more new lesions
Stable disease (SD)	Those who fulfilled the criteria for neither PR and PD

Appendix 8

Risks Associated with Atezolizumab and Guidelines for Management of Adverse Events Associated with Atezolizumab

Toxicities associated or possibly associated with atezolizumab treatment should be managed according to standard medical practice. Additional tests, such as autoimmune serology or biopsies, should be used to evaluate for a possible immunogenic etiology.

Although most immune-mediated adverse events observed with immunomodulatory agents have been mild and self-limiting, such events should be recognized early and treated promptly to avoid potential major complications. Discontinuation of atezolizumab may not have an immediate therapeutic effect, and in severe cases, immune-mediated toxicities may require acute management with topical corticosteroids, systemic corticosteroids, or other immunosuppressive agents.

The investigator should consider the benefit–risk balance a given patient may be experiencing prior to further administration of atezolizumab. In patients who have met the criteria for permanent discontinuation, resumption of atezolizumab may be considered if the patient is deriving benefit and has fully recovered from the immune-mediated event. Patients can be re-challenged with atezolizumab only after approval has been documented by both the investigator (or an appropriate delegate) and the Medical Monitor.

DOSE MODIFICATIONS

There will be no dose modifications for atezolizumab in this study.

TREATMENT INTERRUPTION

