Atezolizumab treatment may be temporarily suspended in patients experiencing toxicity considered to be related to study treatment. If corticosteroids are initiated for treatment of the toxicity, they must be tapered over ≥ 1 month to ≤ 10 mg/day oral prednisone or equivalent before atezolizumab can be resumed. If atezolizumab is withheld for > 105 days after event onset, the patient will be discontinued from atezolizumab. However, atezolizumab may be withheld for > 105 days to allow for patients to taper off corticosteroids prior to resuming treatment. Atezolizumab can be resumed after being withheld for > 105 days if the Medical Monitor agrees that the patient is likely to derive clinical benefit. Atezolizumab treatment may be suspended for reasons other than toxicity (e.g., surgical procedures) with Medical Monitor approval. The investigator and the Medical Monitor will determine the acceptable length of treatment interruption.

MANAGEMENT GUIDELINES

PULMONARY EVENTS

Dyspnea, cough, fatigue, hypoxia, pneumonitis, and pulmonary infiltrates have been associated with the administration of atezolizumab. Patients will be assessed for

Appendix 8

Risks Associated with Atezolizumab and Guidelines for Management of Adverse Events Associated with Atezolizumab (cont.)

pulmonary signs and symptoms throughout the study and will also have computed tomography (CT) scans of the chest performed at every tumor assessment.

All pulmonary events should be thoroughly evaluated for other commonly reported etiologies such as pneumonia or other infection, lymphangitic carcinomatosis, pulmonary embolism, heart failure, chronic obstructive pulmonary disease, or pulmonary hypertension. Management guidelines for pulmonary events are provided in [Table 1](#).

Table 1 Management Guidelines for Pulmonary Events, Including Pneumonitis

Event	Management
Pulmonary event, Grade 1	
 • Continue atezolizumab and monitor closely. • Re-evaluate on serial imaging. • Consider patient referral to pulmonary specialist.

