Pulmonary event, Grade 2	
 • Withhold atezolizumab for up to 12 weeks after event onset.^a • Refer patient to pulmonary and infectious disease specialists and consider bronchoscopy or BAL. • Initiate treatment with 1–2 mg/kg/day oral prednisone or equivalent. • If event resolves to Grade 1 or better, resume atezolizumab.^b • If event does not resolve to Grade 1 or better while withholding atezolizumab, permanently discontinue atezolizumab and contact Medical Monitor.^c • For recurrent events, treat as a Grade 3 or 4 event.
Pulmonary event, Grade 3 or 4	
 • Permanently discontinue atezolizumab and contact Medical Monitor.^c • Bronchoscopy or BAL is recommended. • Initiate treatment with 1–2 mg/kg/day oral prednisone or equivalent. • If event does not improve within 48 hours after initiating corticosteroids, consider adding an immunosuppressive agent. • If event resolves to Grade 1 or better, taper corticosteroids over ≥ 1 month.

BAL = bronchoscopic alveolar lavage.

- ^a Atezolizumab may be withheld for a longer period of time (i.e., > 12 weeks after event onset) to allow for corticosteroids (if initiated) to be reduced to ≤ 10 mg/day oral prednisone or equivalent. The acceptable length of the extended period of time must be agreed upon by the investigator and the Medical Monitor.
- ^b If corticosteroids have been initiated, they must be tapered over ≥ 1 month to ≤ 10 mg/day oral prednisone or equivalent before atezolizumab can be resumed.
- ^c Resumption of atezolizumab may be considered in patients who are deriving benefit and have fully recovered from the immune-mediated event. Patients can be re-challenged with atezolizumab only after approval has been documented by both the investigator (or an appropriate delegate) and the Medical Monitor.

Appendix 8

Risks Associated with Atezolizumab and Guidelines for Management of Adverse Events Associated with Atezolizumab (cont.)

HEPATIC EVENTS

Immune-mediated hepatitis has been associated with the administration of atezolizumab. Eligible patients must have adequate liver function, as manifested by measurements of total bilirubin and hepatic transaminases, and liver function will be monitored throughout study treatment. Management guidelines for hepatic events are provided in [Table 2](#).

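### Section 5.1.3 and Appendix 8 give different clocks, limits and outcomes for an adverse-event hold, and the protocol does not say which governs

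*Protocol*

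**What the plan says.** The protocol limits an adverse-event hold in three places.

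- **Section 5.1.3** covers any adverse event. The patient is discontinued on this condition: "If Atezolizumab is held because of adverse events for > 105 days beyond when the next dose would have been given". The only extension it gives for an adverse-event hold is for a steroid taper: "If a patient must be tapered off steroids used to treat adverse events, Atezolizumab may be held for additional time beyond 105 days".
- **Appendix 8, Treatment Interruption**, covers a narrower group: "Atezolizumab treatment may be temporarily suspended in patients experiencing toxicity considered to be related to study treatment". The number of days is the same but the clock is not: "If atezolizumab is withheld for > 105 days after event onset, the patient will be discontinued from atezolizumab". A steroid-taper extension follows, and then a separate sentence with no mention of a taper: "Atezolizumab can be resumed after being withheld for > 105 days if the Medical Monitor agrees".
- **Appendix 8, event tables**, give many listed events and grades a shorter limit: "Withhold atezolizumab for up to 12 weeks after event onset". Footnote a lengthens it only so that corticosteroids can be reduced. The consequence is stated as "If event does not resolve to Grade 1 or better while withholding atezolizumab, permanently discontinue atezolizumab and contact Medical Monitor". Return after that needs the re-challenge route in the Appendix 8 introduction, repeated in footnote c: "In patients who have met the criteria for permanent discontinuation, resumption of atezolizumab may be considered if the patient is deriving benefit". That route also requires full recovery and approval documented by both the investigator and the Medical Monitor.

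Three rows of Table 4 (symptomatic hypothyroidism, symptomatic hyperthyroidism, Grade 3 or 4 hyperglycemia) say to withhold but give no time limit and name no steroid.

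The cross-references do not rank these texts. The synopsis and Section 4.3.2 send the reader to Section 5.1.3 and the Investigator's Brochure for interruption and discontinuation. Sections 5.1.1 and 5.1.4 send the reader to Appendix 8 and the Brochure.

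**The concern.** A treatment-related event falls under both general rules at once. They start counting on different days, and they say different things about a patient who passes the limit. For a listed event and grade, a third and shorter limit applies as well. These rules decide whether a patient comes off study drug and whose agreement is needed to restart, so two sites could each follow the protocol and handle the same patient differently. Section 9.2 asks investigators to document and explain deviations, but the text does not let them tell whether a given restart is one.

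**Working it through.** This is a consistency check; no error rate, power or sample size enters. The limits are put on one scale, days after event onset.

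**Inputs.** Section 5.1.3: more than 105 days from the date the next dose was due. Appendix 8 general text: more than 105 days from onset. Appendix 8 tables: 12 weeks from onset. Cycle length: 21 days, ±3 (Section 3.1).

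**Formulas.** Let d be the days from onset to the first due dose that is held.

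- Section 5.1.3 limit = 105 + d
- Appendix 8 general text = 105
- Appendix 8 table rows = 12 × 7 = 84

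The base assumption is that the hold starts at the first dose due after onset, so d runs from 0 to 21.

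| d | Section 5.1.3 | Appendix 8 text | Table rows | 5.1.3 minus text | 5.1.3 minus rows |
|---|---|---|---|---|---|
| 0 | 105 | 105 | 84 | 0 | 21 |
| 7 | 112 | 105 | 84 | 7 | 28 |
| 14 | 119 | 105 | 84 | 14 | 35 |
| 21 | 126 | 105 | 84 | 21 | 42 |

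With the +3-day window, d = 24 and the Section 5.1.3 limit is 129. If one further dose is given after onset, d runs from 21 to 42 and the limit from 126 to 147 (without the window). The Appendix 8 text is itself 105 − 84 = 21 days later than its own table rows. The two general rules agree on the day only when d = 0.

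**Count of 12-week rows.** Tables 1, 2, 5, 6, 9, 10 and 12 have one each (7), and Tables 3, 4, 8 and 13 have two each (8): 15 rows in 11 tables. Nine prescribe systemic steroids. Four make them conditional (diarrhea or colitis Grade 2, myocarditis Grade 2, amylase or lipase Grade 3 or 4, myositis Grade 2). Two name no systemic steroid (ocular Grade 2, which is topical only, and neuropathy Grade 2). So 4 + 2 = 6 rows do not prescribe a systemic steroid outright. Where a taper is under way, all three texts allow a longer hold.

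**Example that does not use the 12-week rows.** Take related symptomatic hypothyroidism with onset 14 days before the next due dose, no dose after onset and no steroid. Here d = 14, so the limits are day 119 (Section 5.1.3) and day 105 (Appendix 8 text).

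- *Controlled on day 110.* 110 ≤ 119, so the hold is inside Section 5.1.3. 110 > 105, so it is past Appendix 8, and a restart needs the Medical Monitor's agreement there but not under Section 5.1.3.
- *Controlled on day 130.* 130 exceeds both limits. Section 5.1.3 says the patient is discontinued; Appendix 8 still allows a restart if the Medical Monitor agrees.

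**The case against.** Four points deserve an answer.

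1. *The restart sentence in Appendix 8 may belong to the steroid taper described just before it.* On that reading both general rules have 105 days and a taper extension, and the day-130 difference goes. But the sentence carries no taper condition, and the clocks would still differ. On day 110 the example patient would then be inside Section 5.1.3 and discontinued under Appendix 8, which is a sharper conflict.
2. *The tables may be stricter event-specific limits inside a general cap.* The limits are ceilings, and all can be met together. That is a possible reading, but no protocol text states it. It does not settle Section 5.1.3 against the Appendix 8 text, and for the three Table 4 rows without a limit only those two general rules bound the hold.
3. *The general re-challenge route in Appendix 8 could also serve a patient discontinued under Section 5.1.3.* This narrows the gap without closing it. The route needs full recovery and two documented approvals, and Section 5.1.3 does not call its discontinuation permanent.
4. *The headings suggest a division: general holds in Section 5.1.3, specific events in Appendix 8.* Section 5.1.4 is titled for the management of specific events, and Section 1.3.2 points to it. But the synopsis and Section 4.3.2 send both subjects to Section 5.1.3, and Appendix 8 has its own general interruption rule.

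What stands is that the reach is limited. The conflict concerns related or listed events, and for the listed rows it matters mainly when no taper is under way. The Investigator's Brochure, to which the protocol also points, was not available, so the finding is about the protocol text only.

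**Conclusion.** The inconsistency is real and sits in the current body text. For a related event the two general rules differ by d days, 0 to 21 on the base assumption, and they differ on whether a patient past the limit may return. The 12-week rows are 21 to 42 days shorter than Section 5.1.3. The day ranges assume a 21-day cycle with the hold starting at the first dose due after onset. The difference in outcome takes the Appendix 8 restart sentence as written; the difference in clocks does not depend on that reading. For an unrelated adverse event outside the tables only Section 5.1.3 applies, and there is no conflict. The point should be corrected because it governs when patients come off study drug.

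**What to change.** Reconcile Section 5.1.3, the introduction and Treatment Interruption text of Appendix 8, and the 12-week table rows, so that the limit, the start of the clock and the condition for resuming agree. Alternatively, state which passage takes precedence for each class: any adverse event, related toxicity, a listed event and grade, and the three Table 4 rows with no limit. Align the cross-references in the synopsis and Sections 4.3.2 and 5.1.4. The sponsor's clinicians choose the values; this review proposes none.

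The cost is a wording correction in those places and a letter to sites, with no change to data collection. Section 9.6 requires ethics committee approval, and regulatory approval where locally required, before a change that is neither administrative nor needed to remove an immediate hazard. Altering a limit, clock or restart condition would therefore probably go through as a protocol amendment.

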5.1.4 Management of Specific Adverse Events

Refer to Appendix 8 and Section 6 of the Atezolizumab Investigator's Brochure for a detailed description of anticipated safety risks for atezolizumab.

5.2 SAFETY PARAMETERS AND DEFINITIONS

Safety assessments will consist of monitoring and recording adverse events, including serious adverse events and non-serious adverse events of special interest, performing protocol-specified safety laboratory assessments, measuring protocol-specified vital signs, and conducting other protocol-specified tests that are deemed critical to the safety evaluation of the study.

Certain types of events require immediate reporting to the Sponsor, as outlined in Section 5.4.

5.2.1 Adverse Events

According to the ICH guideline for Good Clinical Practice, an adverse event is any untoward medical occurrence in a clinical investigation subject administered a pharmaceutical product, regardless of causal attribution. An adverse event can therefore be any of the following:

- Any unfavorable and unintended sign (including an abnormal laboratory finding), symptom, or disease temporally associated with the use of a medicinal product, whether or not considered related to the medicinal product
- Any new disease or exacerbation of an existing disease (a worsening in the character, frequency, or severity of a known condition), except as described in Section 5.3.5.8
- Recurrence of an intermittent medical condition (e.g., headache) not present at baseline
- Any deterioration in a laboratory value or other clinical test (e.g., ECG, X-ray) that is associated with symptoms or leads to a change in study treatment or concomitant treatment or discontinuation from study drug
- Adverse events that are related to a protocol-mandated intervention, including those that occur prior to assignment of study treatment (e.g., screening invasive procedures such as biopsies)

